
10.0 Risks/Benefits

10.1. Risks

There is potential loss of confidentiality associated with participation in the proposed study. In terms of loss of confidentiality, quantitative data from participants will need to be stored. Though rigorous and well-tested data safety and security guidelines will be observed, there is still a chance that confidentiality could be breached and sensitive medical information could become known to persons outside the research team.

10.2. Benefits

There are no anticipated benefits to the participants.

10.3 Payments and Costs

Patients participating in the first aim will be paid \$30 and those participating in the second aim will be paid \$50 for their participation in the form of gift cards. For Aim 1, participants will receive the gift cards immediately following the interviews. For Aim 2, participants will be paid for completion of the post-intervention assessment. Oncologists will not be reimbursed for their participation.

11.0 Data Safety and Monitoring

Only adverse events (AEs) related to the study intervention or procedures will be reported. In other words, AEs related to cancer treatment will not be reported.

11.1. Adverse Event Reporting Requirements

11.1.1. Adverse events will be reported using the URCC Adverse Event form and/or as required by the Cancer Center Clinical Trials Office.

	Grade 1	Grade 2		Grade 3				Grade 4		Grade 5		
		Unexpected		Expected	Unexpected		Expected		Unexpected	Expected	Unexpected	Expected
	Unexpected and Expected	with hospitalization	without hospitalization		with hospitalization	without hospitalization	with hospitalization	without hospitalization				
Unrelated	Not Required	Not Required	Not Required	Not Required	Not Required	Not Required	Not Required	Not Required	10 Calendar Days	Not Required	10 Calendar Days	10 Calendar Days
Unlikely	Required	Required	Required	Required	Required	Required	Required	Required				
Possible	Not Required	Not Required	Not Required	Not Required	10 Calendar Days	10 Calendar Days	Not Required	Not Required	5 Calendar Days	10 Calendar Days	5 Calendar Days	10 Calendar Days
Probable												
Definite												

Hospitalization is defined as initial hospitalization or prolongation of hospitalization for ≥ 24 hours, due to adverse event.

11.1.2. Adverse events will be reported in accordance with the following guidelines:

11.1.3. Adverse event reports will be submitted in one of the following ways:

(1) By email: (pdf)

(2) By mail:

(3) By fax:

11.1.4. An unexpected adverse event is defined as any adverse experience, the specificity or severity of which is not consistent with the risk information. This is a minimal risk study as both exercise and mobile app-driven interventions have been shown to improve outcomes in community-dwelling older adults.

11.1.5. A serious event refers to any event in which the outcome results in any of the following: death, a life-threatening adverse experience, inpatient hospitalization or prolongation of existing hospitalization, a persistent or significant disability, incapacity, or a congenital anomaly/birth defect. Important medical events that may not result in death, be life-threatening, or require hospitalization may be considered a serious adverse drug experience when, based upon appropriate medical judgment, they may jeopardize the participant and may require medical or surgical intervention to prevent one of the outcomes listed in this definition. We anticipate that any serious events will be related to standard of care cancer treatments and not due to the intervention. We will not collect adverse events related to cancer treatments.

11.1.6. Adverse events will be reported in accordance with institutional policies (University of Rochester, Research Subject Review Board, local IRB, URCC CCOP, CTO, and DSMB) as per their requirements.

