7.2.2.1. Physical Function and Functional Status (Baseline Only - Patient)

Short Physical Performance Battery (SPPB; baseline only): The SPPB is an objective physical assessment evaluating lower extremity physical function. It is comprised of a four-meter walk, repeated chair stands and a balance test. Impairment on SPPB testing has been shown to be predictive of short-term mortality and nursing home admission in community-dwelling older adults.⁴⁶ If in-person SPPB cannot be performed, we will

perform the virtual SPPB via the phone/zoom, which evaluates the participants' perceived ability to perform above tests (walking, repeated chair stands, and balance).⁴⁷

Activities of daily living (ADL): ADLs are measures of self-care. ADL independence will be assessed using the Katz Index of Independence in Activities of Daily Living, commonly referred to as the Katz ADL. The Katz ADL is the most appropriate instrument to assess functional status as a measurement of the client's ability to perform activities of daily living independently. Clinicians typically use the tool to detect problems in performing activities of daily living and to plan care accordingly. The Index ranks adequacy of performance in the six functions of *bathing, dressing, toileting, transferring, continence, and feeding*. Clients are scored yes/no for independence in each of the six functions. A score of 6 indicates full function, 4 indicates moderate impairment, and 2 or less indicates severe functional impairment.⁴⁸

Instrumental Activities of Daily Living (IADL): Self-reported functional status will be assessed using the IADL subscale of the Multidimensional Functional Assessment Questionnaire: Older American Resources and Services (OARS). The IADL subscale consists of seven questions rated on a three-point Likert scale. It measures the degree to which an activity can be performed independently.⁴⁹

Fall History: A self-reported history of falls in the past three months will be recorded. A history of a recent fall has been demonstrated to be independently predictive of increased risk for chemotherapy toxicity in older cancer patients.⁵⁰

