11.2. Data Safety Monitoring

11.2.1. All adverse events requiring reporting will be submitted to the current Project Coordinator as described in Section 11.1. Serious adverse event reports will be forwarded to the study chair and the Data Safety and Monitoring Committee (DSMC). Adverse events are entered into a protocol-specific spreadsheet.

11.2.2. Adverse event rates are monitored utilizing the spreadsheet. If a serious adverse event is reported frequently, the study chair will conduct a detailed review. The DSMC Committee Chair will be notified and will determine if further action is required.

11.2.3. The Data Safety Monitoring Committee (DSMC) will review study progress and cumulative reports of adverse events every year and as needed. An overall assessment of accrual and adverse events will enable the committee members to assess whether significant benefits or risks are occurring that would warrant study closure.

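### The 11.1.1 table requires no report for some study-related events with hospitalization, mainly at grade 2, although 11.1.5 makes them serious, so their report to the DSMC is not assured

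*Combined protocol and SAP*

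**What the plan says.** Four parts of section 11 bear on this point.

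- **Section 11.0** restricts reporting to events related to the study intervention or procedures and says that those will be reported. It makes no exception by grade.
- **Section 11.1.1** crosses attribution with grade, expectedness and, in some columns, hospitalization. The row for related events begins "Possible Not Required Not Required Not Required Not Required 10 Calendar Days 10 Calendar Days Not Required Not Required". The footnote reads "Hospitalization is defined as initial hospitalization or prolongation of hospitalization for ≥ 24 hours, due to adverse event".
- **Section 11.1.5** defines a serious event: "A serious event refers to any event in which the outcome results in any of the following: death, a life-threatening adverse experience, inpatient hospitalization". Its criteria continue with "inpatient hospitalization or prolongation of existing hospitalization, a persistent or significant disability, incapacity, or a congenital anomaly/birth defect". Neither grade nor expectedness appears among the conditions.
- **Section 11.2.1** sets the route: "All adverse events requiring reporting will be submitted to the current Project Coordinator as described in Section 11.1". It then says: "Serious adverse event reports will be forwarded to the study chair and the Data Safety and Monitoring Committee (DSMC").

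Two later steps build on that route. Under 11.2.2 the study chair reviews in detail when a serious event is reported frequently. Under 11.2.3 the DSMC looks at cumulative event reports yearly and as needed, and considers whether closure is warranted.

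**The concern.** Hospitalization alone makes an event serious under 11.1.5, but the table can tell staff that a related event with hospitalization needs no report. If they follow the table, there may be no serious event report to forward under 11.2.1. The chair's review and the DSMC's cumulative review would then rest on a record that can lack part of the related serious events, which are the ones a monitoring committee most needs to see.

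Such an event is conceivable here. The Short Physical Performance Battery in 7.2.2.1 is a physical test: "It is comprised of a four-meter walk, repeated chair stands and a balance test". Section 9.1 schedules it, or its virtual form, in both aims. An older patient could fall during the in-person version and be admitted.

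**Working it through.** No sample size or error rate is involved, so the check sets the passages side by side.

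**1. Table layout.** The third header line starts "Unexpected and Expected with hospitalization without hospitalization". The second header line pairs unexpected with expected inside each grade, which gives:

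- grade 1: 1 column
- grade 2: 2 unexpected + 1 expected = 3
- grade 3: 2 unexpected + 2 expected = 4
- grade 4: 1 + 1 = 2
- grade 5: 1 + 1 = 2

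Total: 1 + 3 + 4 + 2 + 2 = 12. The row for related events also has 12 entries (4 not required, 2 at 10 days, 2 not required, 4 with deadlines), so entries and columns match one to one.

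This layout is inferred. The extracted grade line itself spans 1 + 2 + 4 + 2 + 3 = 12, which would leave grade 2 with no expected column. Columns 2 and 7 keep their grade under either reading. Column 4 is grade 2 expected only under the inferred layout.

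**2. The row for related events** (Possible, with Probable and Definite blank beneath it):

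| Column | Class | Entry |
|---|---|---|
| 1 | Grade 1 | Not required |
| 2 | Grade 2 unexpected, with hospitalization | **Not required** |
| 3 | Grade 2 unexpected, without | Not required |
| 4 | Grade 2 expected, not split by hospitalization | **Not required** |
| 5 | Grade 3 unexpected, with hospitalization | 10 days |
| 6 | Grade 3 unexpected, without | 10 days |
| 7 | Grade 3 expected, with hospitalization | **Not required** |
| 8 | Grade 3 expected, without | Not required |
| 9, 10 | Grade 4 unexpected, expected | 5 days, 10 days |
| 11, 12 | Grade 5 unexpected, expected | 5 days, 10 days |

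**3. Are these events serious?** The table counts a hospital stay of at least 24 hours due to the event. That falls inside the 11.1.5 criterion, so every event in columns 2 and 7 is serious by the protocol's own definition. So is any hospitalized event in column 4.

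**4. Does the table give hospitalization any weight?** In this row the with/without pairs are identical: columns 2 and 3 not required, columns 5 and 6 at 10 days, columns 7 and 8 not required. A related, unexpected grade 3 event without hospitalization is due in 10 days, while a related, unexpected grade 2 event with hospitalization is not due at all.

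**5. Which cells could be filled in practice?** Section 11.1.4 calls an event unexpected when it does not fit the risk information, and 10.1 lists only loss of confidentiality. A related physical injury would therefore be unexpected. Column 7 has little practical content, and the same reasoning leaves little in column 4. The gap that matters is mainly column 2.

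**6. The 24-hour footnote.** Section 11.1.5 sets no minimum stay. Because each with/without pair is identical, this difference changes no entry in the present table. It would matter once the entries depend on hospitalization.

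**The case against.** The strongest reply is that the table is not the only way for an event to be recorded or reported.

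- Section 11.2.1 also says, without limiting it to reportable events, that adverse events go into a study spreadsheet, and 11.2.2 monitors rates from it.
- Section 11.0 promises that related events will be reported.
- Section 11.1.1 adds Clinical Trials Office requirements, and 11.1.6 adds those of the review board and other bodies.
- The table's positive entries are all deadlines, so it can be read as governing timed reports only. An entry of *Not Required* there does not forbid a report owed elsewhere.

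Much of this stands. A reader might infer that these events are not reportable at all, or that the table is the DSMC's only source. The documents support neither inference. What remains is that none of these provisions states a rule for the affected cells, a spreadsheet entry is not the forwarding of a serious event report, and the content of the institutional policies is not in the documents. Section 11.0 does not settle the matter either, because it is one side of the conflict.

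Three further cautions are fair. The fall example needs the event to be graded 2; section 11 names no grading scale, and at grade 3 unexpected the table already requires a report. The physical test may also be done virtually. And the table is visibly damaged in extraction, so a hospitalization split that never changes an entry is itself a reason to look at the original PDF.

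**Conclusion.** The point holds as an inconsistency among the 11.1.1 table and sections 11.0, 11.1.5 and 11.2.1. Two with-hospitalization cells in the row for related events, plus the unsplit grade 2 expected column, carry no reporting requirement although they can hold events that the protocol defines as serious. The consequence is limited: such an event, mainly at grade 2, *can* fail to produce a report to the DSMC. It does not follow that it *will*.

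The practical impact is small. The protocol calls this a minimal-risk study and anticipates that serious events will come from standard cancer treatment. No aim, endpoint or analysis is affected. A reader might want to express one missed event as a percentage of the patients enrolled, but the documents give no expected event rate, so that figure would be an illustration and not an estimate.

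The conclusion assumes that the extracted cells match the original table and that its columns follow the second header line.

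**What to change.** First check the row for related events against the original PDF. If the cells are as extracted:

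1. Add one overriding line to 11.1.1: any event that is possibly, probably or definitely related and meets the 11.1.5 definition is reported and forwarded to the DSMC, regardless of grade or expectedness.
2. Change the grade 2 unexpected and grade 3 expected with-hospitalization cells to match, and split or footnote the grade 2 expected column so that hospitalized events are covered.
3. Use one definition of hospitalization in the table footnote and in 11.1.5, since the new line would make the difference matter.
4. Confirm that 11.0 and 11.2.1 read consistently with the result, including whether the spreadsheet holds all related events or only reportable ones.

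The cost is a short protocol amendment and a few table entries. Very few extra reports should follow in a study of this size and risk.

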11.2. Data Safety Monitoring

11.2.1. All adverse events requiring reporting will be submitted to the current Project Coordinator as described in Section 11.1. Serious adverse event reports will be forwarded to the study chair and the Data Safety and Monitoring Committee (DSMC). Adverse events are entered into a protocol-specific spreadsheet.

11.2.2. Adverse event rates are monitored utilizing the spreadsheet. If a serious adverse event is reported frequently, the study chair will conduct a detailed review. The DSMC Committee Chair will be notified and will determine if further action is required.

11.2.3. The Data Safety Monitoring Committee (DSMC) will review study progress and cumulative reports of adverse events every year and as needed. An overall assessment of accrual and adverse events will enable the committee members to assess whether significant benefits or risks are occurring that would warrant study closure.

